1.5. Dose Selection Rationale

Doses up to 40 mg/kg/day were given in the Phase 1/2 PK study (Protocol INS011-14-029) and the long-term safety study (Protocol INS011-14-030). The maximum dose given was 3200 mg/day in an adolescent. These doses were generally well tolerated even without titration. Only six subjects required a decrease in dose due to somnolence (2), abdominal pain (1), diarrhea (1), irritability (1), and seizure (1).

An interim safety report was generated for the long-term safety study (INS011-14-030) with a data cut off of 31 Jan 2017. As of the data cut off, 52 patients (9 infants, 26 children, and 17 adolescents) were enrolled and had received at least one dose of the investigational product in this study. As of the data cut-off, the mean modal dose (defined as the dose with the longest duration) for all patients was 23.47 mg/kg/day, and the mean number of days on-study for all patients was 220.6 (Table 2). Overall, seven patients (13.5%) had dose reductions resulting from an AE, and 3 patients (5.8%) had dose reductions due to other reasons (Table 3). The frequency of dose reductions was greater in the patients receiving 40 mg/kg/day compared with patients receiving 10 mg/kg/day (seven patients [35.0%] and two patients [14.3%], respectively). Overall, one patient (1.9%) was taking <10 mg/kg/day, 10 patients (19.2%) were taking between 10 and <20 mg/kg/day, 20 patients (38.5%) were taking between 20 and <40 mg/kg/day, and 20 patients (38.5%) were taking 40 mg/kg/day as of the data cut-off (Table 4). Therefore, this study will evaluate the doses of 20 mg/kg/day, 30 mg/kg/day and 10 mg/kg/day. Doses higher than 20 mg/kg/day will be titrated.

Table 2: Cannabidiol Oral Solution Exposure (Study INS011-14-030)

	Infants (N=9)	Children (N=26)	Adolescents (N=17)	All Patients (N=52)
Modal Dose (mg/kg/day)^a				
n	9	26	17	52
Mean (SD)	31.11 (10.541)	21.17 (12.719)	22.94 (12.127)	23.47 (12.488)
Median	40.00	20.00	20.00	20.00
Min, Max	20.0, 40.0	0.5, 40.0	10.0, 40.0	0.5, 40.0
Total Duration of Study Drug at Any Dose (Days)				
n	9	26	17	52
Mean (SD)	234.1 (91.73)	210.0 (118.73)	229.7 (95.47)	220.6 (105.86)
Median	253.0	249.0	250.0	250.5
Min, Max	1, 336	1, 344	1, 336	1, 344

Abbreviations: BID = twice daily; Max = maximum; Min = minimum; N = total number; n = sample size; SD = standard deviation.

^a For each patient, the modal dose corresponds to the dose with the longest duration.

Duration = Date of last dose – date of first Dose + 1.

The study drug is Cannabidiol Oral Solution (300 mg/mL) administered BID

Age Category: Infants = 1 to <2 years of age, Children = 2 to <12 years of age, Adolescents = 12 to ≤17 years of age. Age categories are based on the patient's age at the beginning of their previous study (INS011-14-029).

Source: Interim Safety Report for Study INS011-14-030.

Table 3: Cannabidiol Oral Solution Dose Reduction by Initial Planned Dose (Study INS011-14-030)

	10 mg/kg/day (N=14)	20 mg/kg/day (N=18)	40 mg/kg/day (N=20)	All Patients (N=52)
Number of patients with ≥ 1 dose reductions	2 (14.3%)	0	7 (35.0%)	9 (17.3%)
Reason for dose reductions				
Adverse event	1 (7.1%)	0	6 (30.0%)	7 (13.5%)
Lack of efficacy	0	0	0	0
PK analysis result	0	0	0	0
Other	1 (7.1%)	0	2 (10.0%)	3 (5.8%)

The study drug is Cannabidiol Oral Solution (300 mg/mL) administered BID

Patients having more than 1 dose reduction due to the same reason are counted only once for this reason.

Patients may be included in more than 1 reason for dose reduction.

Source: Interim Safety Report for Study INS011-14-030.

Table 4: Distribution of Patients by Cannabidiol Oral Solution Dose (Study INS011-14-030)

	Infants (N=9)	Children (N=26)	Adolescents (N=17)	All Patients (N=52)
Number of patients taking dose as of cut-off				
<10 mg/kg/day	0	1 (3.8%)	0	1 (1.9%)
10 -<20 mg/kg/day	0	7 (26.9%)	3 (17.6%)	10 (19.2%)
20 -<40 mg/kg/day	3 (33.3%)	9 (34.6%)	8 (47.1%)	20 (38.5%)
≥ 40 mg/kg/day	6 (66.7%)	8 (30.8%)	6 (35.3%)	20 (38.5%)

The study drug is Cannabidiol Oral Solution (300 mg/mL) administered BID

Age Category: Infants = 1 to <2 years of age, Children = 2 to <12 years of age, Adolescents = 12 to ≤ 17 years of age. Age categories are based on the patient's age at the beginning of their previous study (INS011-14-029).

Source: Interim Safety Report for Study INS011-14-030.

1.6. Summary of Potential Risks and Benefits

As reviewed in [Section 1.2](#) and [Section 1.3](#), numerous nonclinical and clinical studies have examined other formulations of CBD. Several areas of potential concern have been identified with the use of CBD, especially in nonclinical studies. These include:

- Competitive binding of CYP proteins (thus, an impact on drug metabolism in the liver). Cannabidiol is metabolized predominantly by CYP3A4 and CYP 2C19. Cannabidiol may inhibit these 2 isozymes, as well as having small effects on CYP3A5, CYP1A1, and CYP2C9.
- Potential downregulation of immune responses involving the T, B, T-helper, and T cytotoxic subsets of leukocytes and/or those dependent on IL-2 or IFN- γ .

Based on recent studies of cannabinoid administration in humans, controlled CBD may be safe in humans and animals. However, further studies are needed to clarify these reported *in vitro* and *in vivo* side-effects.³⁹

The inclusion/exclusion criteria, concomitant medication guidelines, and safety monitoring (AEs, clinical laboratory, vital signs, ECG, and physical examination assessments) planned for this study are intended to minimize these potential safety risks.

Criteria for removal of subjects from the study will dictate discontinuation of patient participation should a safety issue arise (see [Section 3.3](#)).

Two facets of the current treatment landscape for pediatric patients with treatment-resistant absence seizures support the potential benefit for subjects in this study. First, pediatric patients with treatment-resistant absence seizures continue to experience a significant unmet medical need despite ongoing treatment with currently available medications and procedures. Patients included in this study may potentially benefit from treatment with Cannabidiol Oral Solution. Devinsky et al.⁴⁰ recently noted that pediatric subjects with treatment-resistant seizures are particularly good candidates for CBD intervention. Data reviewed in [Section 1.2.2](#) and [Section 1.3.4](#) demonstrate that CBD has shown preliminary efficacy in treating epilepsy in several early-stage nonclinical and clinical studies, respectively. This study is expected to serve as a critical step in the development of Cannabidiol Oral Solution as a treatment for refractory childhood absence epilepsy.

Second, synthetic pharmaceutical grade Cannabidiol Oral Solution is expected to have several distinct advantages over cannabis plant-derived extracts:

- Availability of the drug substance does not depend on cannabis plant production. As such, the development of Cannabidiol Oral Solution will not support growth and distribution of plants from which marijuana is derived.
- Manufacture of Cannabidiol Oral Solution does not involve an extraction process whereby the derived constituents could also include a significant amount of Δ^9 -THC. The manufacturing process can be controlled so that mass quantities can be produced that are uniform in quality, purity, and consistency and can be delivered in known and predetermined quantities.

Insys Development Company, Inc.

Protocol Number INS011-17-103

- Variability in concentration and constituents should be reduced among batches, which may improve safety and tolerability.
- Reduced concern for contamination by Δ^9 -THC, herbicides, pesticides, etc.

Approved

Insys Development Company, Inc.
Protocol Number INS011-17-103

2. STUDY OBJECTIVES

2.1. Primary Objective

- To assess the efficacy of Cannabidiol Oral Solution in the treatment of pediatric patients with treatment-resistant childhood absence seizures.

2.2. Secondary Objectives

- To assess any improvement in qualitative assessments of patient status over the duration of the study.
- To assess the safety and tolerability of Cannabidiol Oral Solution treatment in pediatric patients with treatment-resistant childhood absence seizures.
- To assess the pharmacokinetics of Cannabidiol Oral Solution in pediatric patients with treatment-resistant childhood absence seizures.

Insys Development Company, Inc.
Protocol Number INS011-17-103

3.1.1. Titration and Treatment Periods

Thirty patients in total will be enrolled into one of three dose cohorts; ten patients per cohort. Patients in Cohort 1 will be treated before patients are treated in Cohort 2, and patients in Cohort 2 will be treated prior to patients being treated in Cohort 3. Patients will be dosed approximately every 12 hours with food to help ensure consistent plasma levels are achieved, except for Visit 6 (Week 4, Day 7) when blood for fasting pharmacokinetic (PK) analysis will be drawn prior to the morning dose.

- Cohort 1: 20 mg/kg/day divided twice daily (BID) for 4 weeks.
- Cohort 2: Titration period of 20 mg/kg/day divided BID for 5 days, followed by 30 mg/kg/day divided BID for 4 weeks.
- Cohort 3: 10 mg/kg/day divided twice daily (BID) for 4 weeks. Eligible patients will be provided with their titration dose during their Baseline Visit (5 days at 20 mg/kg/day for Cohorts 2).

During the Treatment Period, patients will be dosed for 4 weeks during which the investigator will assess tolerability and effect. Patients will return to the site at the end of Week 2 (Visit 4) to evaluate medical status (seizure diary, vital signs, and neurological exam), clinical laboratory assessments, and assess AEs.

At Visit 5 (Week 4, Day 6), the patient will have a repeat 4-hour video-EEG including hyperventilation to count the number of absence seizures captured, and blood for PK analysis

Insys Development Company, Inc.
Protocol Number INS011-17-103

will be drawn. Blood for PK analyses will be drawn at Visit 3, Visit 5 (fed; Week 4, Day 6) and Visit 6 (fasted; Week 4, Day 7), or the Early Withdrawal Visit. The investigator will assess tolerability and efficacy.

Following the completion of the Treatment Period (Visit 6), patients will have the option to continue treatment in an open-label long-term safety study. Patients who choose to enroll in the long-term safety study will not have a follow-up phone call. Patients who do not choose to enroll in the long-term safety study will taper the dose of Cannabidiol Oral Solution according to the following schedule: doses between 20-30 mg/kg/day will be reduced to 20 mg/kg/day for five days and then discontinued; doses \leq 20 mg/kg/day can be discontinued without titration. This can be modified by the investigator based upon the patient's response. Patients will receive a follow-up phone call 14 days after completing Visit 6 (End of Study).

Available safety data will be reviewed on an ongoing basis to ensure doses are generally well tolerated. Details of the safety data review will be provided in the Data Monitoring Charter.

3.1.2. Follow-Up Period

A follow-up phone call will occur 14 days after Visit 6 (End of Study) of the study drug to assess AEs, AEDs, and record concomitant medications.

3.1.3. Study Assessments

Safety assessments for all patients will include medical history, physical examination, vital signs (seated blood pressure, pulse rate, temperature, and respiration rate), clinical laboratory testing (hematology, chemistry, and urinalysis), 12-lead ECG, prior medication history (assessments of past/current AEDs and concomitant medications), C-SSRS, and AE assessments.

A complete physical examination will be done at Screening (Visit 1). A neurological examination (complete at Screening [Visit 1] and brief at all other study visits) and vital signs will be assessed at Screening (Visit 1), Baseline (Visit 2), Treatment Period (Visits 3 [Week 1], 4 [Week 2], and 6 [Week 4, End of Study]), or at the Early Withdrawal Visit. Visit 6 is the End of Study visit for patients who complete the study.

Clinical laboratory blood tests (hematology, chemistry) will be obtained during the Screening (Visit 1), Treatment Period (Visits 3, 4, and 6 [End of Study]) or at the Early Withdrawal Visit. Urinalysis will be obtained during Screening (Visit 1), and at Visit 6 (End of Study) or at the Early Withdrawal Visit. Concomitant AED blood levels will be determined at Baseline (Visit 2), Visit 6 (End of Study), or the Early Withdrawal Visit.

A 12-lead electrocardiogram (ECG), will be completed during Screening (Visit 1), Treatment Period (Visit 6 [End of Study]) or at the Early Withdrawal Visit.

For patients aged 7 to 17 years and if the developmental level is appropriate, the Columbia-Suicide Severity Rating Scale [(C-SSRS) Children's or Adult's version as appropriate based on age] will be utilized to assess suicidality at the following study visits: Screening (Visit 1) and Visit 5 (Week 4, Day 6) or the Early Withdrawal Visit. For patients who are less than 7 years of age or for whom the C-SSRS is inappropriate due to the patient's developmental functioning, a clinical assessment will be made.

Insys Development Company, Inc.
 Protocol Number INS011-17-103

All adverse events (AEs) that arise during the Screening, Titration, Treatment, and Follow-up Periods will be documented. Concomitant medications will be reviewed and documented at each visit. A meal diary will be completed at Baseline (Visit 2), and for 24 hours before each PK sampling visit at Visit 3 and Visit 5 (Week 4, Day 6), or the Early Withdrawal Visit.

To assess PK parameters, blood draws will be obtained at Visit 3, Visit 5 (fed; Week 4, Day 6) and Visit 6 (fasted; Week 4, Day 7), or the Early Withdrawal Visit. Blood draws for PK values at Visits 5 and 6 will occur as follows:

Fasting/Fed	PK Sample Visits	Time points
Fed: Patients should arrive without food and the morning dose. Site provides a high fat/high calorie food then doses patient	Visit 5 (Week 4, Day 6)	Pre-dose (before meal/morning dose) and 2, 4, 6 hours after the morning dose (but before next dose)
Fasted (2 hours before dose until 2 hours after dose): Patients should arrive without food and the morning dose. Site provides a standard meal 2 hours after dose.	Visit 6 (Week 4, Day 7)	Pre-dose and 2 (before meal), 4, 6 hours after the morning dose (but before next dose)

To assess efficacy, a 4-hour video-EEG including hyperventilation will be obtained at the Baseline Visit (Visit 2), Visit 5 (Week 4, Day 6) or the Early Withdrawal Visit. Absence seizures will be counted by an electrophysiologist not involved with the study. Further details will be provided in the video-EEG Charter.

Daily seizure diaries will be completed throughout the Titration and Treatment Periods, or the Early Withdrawal Visit. The daily record will ask: "How many absence seizures did the patient have today?".

To assess efficacy, the Clinical Global Impression – Global Improvement (CGI-I) assessment will be completed by the investigator at Visit 3, Visit 5 (Week 4, Day 6) or the Early Withdrawal Visit. All screening, efficacy, and safety assessments will be performed according to the schedule of assessments summarized in [Table 1](#).

3.2. Patient Selection

3.2.1. Inclusion Criteria

Patients must meet all of the following inclusion criteria

1. Patient and/or parent(s)/caregiver(s) fully comprehend the informed consent form (ICF) and assent form, understand all study procedures, and can communicate satisfactorily with the investigator and study coordinator, in accordance with applicable laws, regulations, and local requirements.
2. Male or female between 3 and 12 years (inclusive) at the time of onset and between 3 and 17 years of age (inclusive) at the time of consent.
3. Body weight ≥ 10 kg.
4. Diagnosed with childhood absence epilepsy (CAE), confirmed by EEG with at least 3 bursts of general spike wave (GSW of 2.7 to 5 hertz lasting ≥ 3 seconds) during the 4-hour EEG, and has had an adequate trial of at least 2 AEDs and are treatment-resistant to at least one AED.
5. Willingness to not start a ketogenic diet during the Baseline or Treatment Period.
6. A female patient is eligible to participate in the study if she is:
 - a. Premenarchal, or
 - b. Of childbearing potential with a negative urine pregnancy test at the Screening Visit. If sexually active, she must agree to fulfill one of the following requirements:
 - i. Complete abstinence from intercourse for 24 weeks prior to administration of the first dose of the investigational product, throughout the Treatment Period, and 2 weeks after completion or premature discontinuation from the investigational product, and agreement to use a double barrier method if she becomes sexually active.
 - ii. Use of acceptable methods of contraception throughout the study and 2 weeks after completion or premature discontinuation from investigational product. The acceptable method of contraception is double barrier method (i.e., condom plus spermicide or a condom plus intrauterine device [IUD], diaphragm, or stable hormonal contraceptive use for at least 3 months before screening and through 28 days after study completion).
7. A sexually active male patient or partner of an enrolled subject must be willing to use acceptable methods of contraception throughout the study and for 2 weeks after completion of study participation or discontinuation from investigational product. The acceptable methods of birth control are abstinence or double barrier birth control (i.e., condom plus spermicide or a condom plus one of the methods listed in [7]).
8. In the opinion of the investigator, the parent(s)/caregiver(s) is willing and able to comply with the study procedures and visit schedules, including venipuncture, and the Follow-up Visits.

9. General good health (defined as the absence of any clinically relevant abnormalities as determined by the investigator) based on physical and neurological examinations, medical history, and clinical laboratory values (hematology, chemistry, and urinalysis) completed during the Screening Visit that would prohibit the patient from safely participating in the trial as judged by the investigator.

3.2.2. Exclusion Criteria

1. Patient or parent(s)/caregiver(s) have daily commitments during the study duration that would interfere with attending all study visits.
2. Has a history of active nonfebrile seizures other than absence seizures (e.g., tonic, atonic, or myoclonic seizures). History of any other seizure type currently in remission must be adjudicated by the medical monitor.
3. Has a history of febrile seizures after 3 years of age.
4. Has a history consistent with juvenile absence epilepsy or juvenile myoclonic epilepsy.
5. Currently taking felbamate
6. Currently taking phenytoin, fluvoxamine, carbamazepine, or St. John's Wort.
7. Currently taking concomitant medications that are strong inhibitors/inducers/sensitive substrates with a narrow therapeutic index for cytochrome P450 3A4 (CYP3A4), CYP2C9, or CYP2C19 [Note: Stable doses of Valproic Acid during the screening, titration, treatment, and follow-up periods are permitted].
8. Currently on a ketogenic diet.
9. In the opinion of the investigator, any clinically significant, unstable medical abnormality, chronic disease, or a history of a clinically significant abnormality of the cardiovascular, gastrointestinal, respiratory, hepatic, or renal systems.
10. Clinically significant abnormal liver function test (LFT) values, including:
 - a. Albumin, direct bilirubin, total bilirubin, aspartate aminotransferase (AST), and alanine aminotransferase (ALT) ≥ 3 times the upper limit of normal (ULN).
11. History or presence of abnormal ECGs that are clinically significant in the opinion of the investigator.
12. Has a current or history of clinically significant intellectual disability or major psychiatric disease, including autism spectrum disorder, which would interfere with compliance.
13. For patients aged 7 to 17 years of age and for whom the C-SSRS is developmentally appropriate, an affirmative answer to queries regarding active suicidal ideation with some intent to act but without a specific plan or active suicidal ideation with a specific plan and intent on the C-SSRS assessment at the Screening Visit. Patients who have significant findings for suicidal ideation as assessed by the C-SSRS must be referred to the investigator for follow-up evaluation.
14. Any history of attempted suicide.

15. Previously received any investigational drug or device or investigational therapy within 30 days before Screening.
16. Taken any cannabinoids (cannabidiol, Δ^9 -tetrahydrocannabinol [Δ^9 -THC], hemp oil, Realm Oil, or marijuana) in the 30 days prior to the Screening Visit.
17. History of an allergic reaction or a known or suspected sensitivity to any substance that is contained in the investigational product formulation.
18. Known infection with hepatitis B, hepatitis C, or human immunodeficiency virus (HIV).
19. In the opinion of the investigator, the patient is unsuitable in any other way to participate in this study.
20. Body weight < 10 kg or > 90 kg.

3.3. Removal of Patients from Therapy or Assessment

Patients will be allowed to discontinue their participation in the study at any time for any reason (withdrawal of consent). Furthermore, participation in this clinical study may be discontinued by the investigator or by the sponsor for any of the following reasons:

- Intolerable side effects of the study product.
- Changes in medical status or medical condition of the patient such that the investigator believes that patient safety will be compromised or that it would be in the best interest of the patient to stop treatment.
- Patient safety or welfare is at risk.
- Non-compliance with study visits, defined as failure to perform any portion of scheduled assessments or procedures.
- Any unforeseen event that in the opinion of the treating physician and/or the Principal investigator, will prevent the research participant from continuing in this study.
- Patient does not tolerate 10 mg/kg/day.
- Sponsor decides to stop the study.

In the event of a patient's withdrawal, the investigator will promptly notify the sponsor. Every effort will be made to complete the end-of-study assessments.

Should any patient choose to withdraw early from the study, they will be advised of the safety precautions to be taken and will be followed until resolution of any AE or until the unresolved AEs are judged by the investigator to have stabilized.

3.4. Dose Adjustment Criteria

Doses will not be adjusted in this study.

3.5. Stopping Rules

The investigator reserves the right to terminate the study in the interests of patient safety and welfare. The Sponsor reserves the right to terminate the study at any time for administrative reasons.

Patients will also be discontinued from the study if they meet the following criteria:

- ALT or AST $> 3 \times$ ULN with (or the appearance of) fatigue, nausea, vomiting, right upper quadrant pain or tenderness, fever, rash, and/or eosinophilia $> 5\%$
- ALT or AST $> 8 \times$ ULN
- ALT or AST $> 5 \times$ ULN for more than 2 weeks
- ALT or AST $> 3 \times$ ULN and bilirubin $> 2 \times$ ULN or INR > 1.5

For patients meeting the above criteria, the investigator will arrange for the patient to return to the investigational site as soon as possible (within 24 hours of notice of abnormal results) for repeat assessment of ALT, AST, bilirubin, and alkaline phosphatase (ALP), detailed history, and physical examination. Patients will be followed until all abnormalities have normalized (in the investigator's opinion) or returned to the baseline state. If the patient is unable to return to the investigational site, repeat assessments may be performed at a local laboratory.

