6.2.6. Clinical Laboratory Assessments

Blood samples for hematology and chemistry assessments will be collected during Screening (Visit 1), Treatment Period (Visits 3, 4, and 6 [End of Study]) or the Early Withdrawal Visit. Urine samples for urinalysis will be collected during Screening (Visit 1), Treatment Period (Visit 6 [End of Study]) or the Early Withdrawal Visit.

- Hematology: hemoglobin, hematocrit, total and differential leukocyte count, red blood cell (RBC), and platelet count.
- Chemistry: albumin, blood urea nitrogen (BUN), creatinine, total bilirubin, alkaline phosphatase (ALP), aspartate transaminase (AST), alanine transaminase (ALT), sodium (Na^+), potassium (K^+), chloride (Cl^-), lactate dehydrogenase (LDH), uric acid, glucose, and calcium.
- Urinalysis: pH, specific gravity, protein, glucose, ketones, bilirubin, blood, nitrite, leukocyte esterase, and urobilinogen. If protein, occult blood, nitrite, or leukocyte esterase values are out of range a microscopic examination will be performed.

Concomitant AED blood levels will be determined at Baseline (Visit 2), Visit 6 (End of Study), or the Early Withdrawal Visit.

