6.2.8. Adverse Events and Serious Adverse Events

6.2.8.1. Definition of Adverse Events

An AE is defined as any untoward medical occurrence in a patient administered a pharmaceutical product during the course of a clinical investigation. An AE can therefore be any unfavorable and unintended sign, symptom, or disease temporally associated with the use of an investigational product, whether or not thought to be related to the investigational product.

Patients will be monitored throughout the study for AEs. Monitoring for treatment-emergent AEs will begin as soon as the patient is dosed. All AEs must be followed until they are resolved or stabilized, or until all attempts to determine resolution of the event are exhausted. The investigator should use their discretion in ordering additional tests as necessary to monitor the progress of such events.

An AE may be:

- A new illness, not documented in the patient's medical history;
- Worsening of a concomitant illness;
- An effect of the study medication; it could be an abnormal laboratory value, as well as a significant shift from baseline within normal range which the qualified investigator or medical qualified designate considers to be clinically important;
- A combination of two or more of these factors.

Surgical procedures themselves are not AEs. They are therapeutic measures for conditions that required surgery. The condition for which the surgery is required is an AE, if it occurs or is detected during the study period. Planned surgical measures permitted by the clinical study protocol and the conditions(s) leading to these measures are not AEs, if the condition(s) was (were) known before the start of study treatment. In the latter case, the condition should be reported as medical history.

Absence seizures will not be considered AEs. However, new seizure types and injury resulting from a seizure will be captured as AEs.

Patients will be monitored throughout the study for AEs. All AEs must be followed until they are resolved or stabilized, or until all attempts to determine resolution of the event are exhausted. The investigator should use his/her discretion in ordering additional tests as necessary to monitor the progress of such events.

Adverse events reported prior to dose administration will be recorded as part of the patient's medical history.

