7.3. Treatment Period

7.3.1. Visit 3 (Day 1)

The following procedures and assessments will be performed on Day 1:

- Review and record seizure diary and meal diary.
- Assessment of past/current AEDs and other concomitant medications.
- Record vital signs (seated blood pressure, pulse rate, temperature, and respiration rate).
- Collect blood samples (clinical chemistry and hematology, and PK sample)
- Perform a brief neurological examination.
- Record height and weight.
- Collect, review, and dispense Cannabidiol Oral Solution. If patient is in Cohort 1 (20 mg/kg/day) or Cohort 3 (10 mg/kg/day), train patient/caregiver to administer and record treatments.
- Dispense seizure diary.
- Investigator complete CGI-I.
- Review AEs.

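### The Section 3.5 stop for ALT or AST > 5 × ULN lasting more than 2 weeks cannot be shown on scheduled chemistry before End of Study, and a first value > 5 × ULN triggers no stated retest

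*Protocol*

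**What the plan says.** Section 3.5 lists four hepatic criteria that require discontinuation. Three can be met on a single blood draw: > 8 × ULN; > 3 × ULN with listed symptoms or eosinophilia > 5%; and > 3 × ULN with bilirubin > 2 × ULN or INR > 1.5. The remaining one needs duration: ALT or AST > 5 × "ULN for more than 2 weeks".

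The same section sets out a repeat assessment, and its entry condition is explicit: "For patients meeting the above criteria, the investigator will arrange for the patient to return to the investigational site as soon as possible". The content is "repeat assessment of ALT, AST, bilirubin, and alkaline phosphatase (ALP), detailed history, and physical examination", and a local laboratory may be used if the patient cannot return to the site.

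On the schedule, Section 6.2.6 states: "Blood samples for hematology and chemistry assessments will be collected during Screening (Visit 1), Treatment Period (Visits 3, 4, and 6 [End of Study"; the only other draw is at Early Withdrawal. Section 3.1.1 fixes the middle visit: "Patients will return to the site at the end of Week 2 (Visit 4"). Table 1 gives Visits 3 and 4 a window of 0 days and Visit 6 a window of ± 3 days.

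Section 7.3.1 indicates when Cohorts 1 and 3 start drug: "If patient is in Cohort 1 (20 mg/kg/day) or Cohort 3 (10 mg/kg/day), train patient/caregiver to administer and record treatments". Under Section 7.2.1 only Cohort 2 receives drug at Baseline, for 5 days of titration at 20 mg/kg/day.

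On other follow-up, Section 6.2.8.1 requires adverse events to be followed until resolved or stabilized and names transaminase elevation as an event of special interest. It adds: "The investigator should use their discretion in ordering additional tests as necessary to monitor the progress of such events".

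**The concern.** A mandatory stopping rule that depends on duration needs blood draws spaced so that the duration can be observed. Here the first two treatment-period draws are too close together to show it, and the third falls at End of Study, when the decision to stop treatment in this trial has little left to act on. Section 3.5 does contain a retest procedure, but it starts only after a criterion has been met, so it cannot supply the second value that the two-week criterion needs.

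At stake is a child with an isolated value > 5 to 8 × ULN who continues dosing without a required second look. Progression to > 8 × ULN, or to the symptom or bilirubin criteria, could be recognized late, and sites may differ in when they retest. The sponsor treats transaminase elevation as an event of special interest. Stable valproate is allowed (Section 3.2.2, exclusion 7), and Section 1.4 itself lists liver failure among that drug's serious side effects.

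**Working it through.** **Inputs.** Visit 3 = Day 1 of the Treatment Period, window 0 (Table 1). Visit 4 = end of Week 2, window 0, taken as Day 14, or Day 15 if read as two full weeks after Day 1. Visit 6 = Week 4, Day 7 = Day 28, window ± 3, so Days 25 to 31. Dosing is twice daily.

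**Can Screening start the clock?** No. Exclusion 10 bars ALT or AST ≥ 3 × ULN at entry.

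**Which scheduled pairs are more than 14 days apart?** Gap = later day − earlier day.

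| Pair | Visit 4 = Day 14 | Visit 4 = Day 15 | More than 14 days? |
|---|---|---|---|
| Visit 3 to Visit 4 | 14 − 1 = 13 | 15 − 1 = 14 | Never |
| Visit 4 to Visit 6, nominal | 28 − 14 = 14 | 28 − 15 = 13 | No |
| Visit 4 to Visit 6, window | 11 to 17 | 10 to 16 | Only if Visit 6 is on Day 29–31 (or 30–31) |
| Visit 3 to Visit 6 | 27 (24 to 30) | 27 (24 to 30) | Yes, but known only at Visit 6 |

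No scheduled pair can show the criterion before End of Study.

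**Who is affected.** The three single-draw criteria catch > 8 × ULN and any value > 3 × ULN with a listed symptom, eosinophilia > 5%, or qualifying bilirubin or INR. What is left is > 5 to 8 × ULN with none of these.

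**First elevation at Visit 3.** In Cohorts 1 and 3 (20 of 30 patients) drug is first dispensed at Visit 3, so that sample is essentially pre-treatment. An on-drug elevation at Visit 3 is therefore mainly a Cohort 2 matter (10 of 30), after 5 days of titration. The earliest day more than 14 days after Day 1 is 1 + 15 = Day 16. At present the earliest scheduled demonstration is Visit 6, Day 25 to 31. The possible gain is 28 − 16 = 12 days nominally (25 − 16 = 9 to 31 − 16 = 15). With a retest within 72 hours and then weekly (Days 4, 11, 18), the first qualifying draw is Day 18, a gain of 28 − 18 = 10 days (7 to 13).

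**First elevation at Visit 4.** The earliest qualifying day is 14 + 15 = Day 29 (or 15 + 15 = Day 30), after nominal end of treatment on Day 28. No retest schedule brings this criterion into nominal treatment. What a retest adds is sight of progression between Visits 4 and 6: 14 days nominally (11 to 17), or 2 × 14 = 28 doses (22 to 34), half of the 28-day Treatment Period. Retests on about Day 17 and Day 24 would put two observations where none is now scheduled.

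**INR.** The scheduled panel opens with "Chemistry: albumin, blood urea nitrogen (BUN), creatinine, total bilirubin, alkaline phosphatase (ALP), aspartate transaminase (AST), alanine transaminase (ALT") and continues through electrolytes and other chemistry, without INR. The repeat panel omits it too. On protocol-specified draws, the fourth criterion can therefore act only through bilirubin.

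**The case against.** The strongest reply is that the protocol already obliges follow-up. Section 6.2.8.1 counts a clinically important abnormal laboratory value as an adverse event and requires adverse events to be followed until resolved or stabilized. Section 6.2.8.8 repeats the duty for events possibly related to treatment. A laboratory event cannot be shown to resolve without another sample. Section 3.3 lets the investigator withdraw a patient on safety grounds at any time, and Section 6.2.8.9 provides ongoing safety review under a Data Monitoring Charter that is not shown. A reader who infers that the protocol leaves such a child unfollowed would be wrong. What stands is narrower: whether the value counts as an adverse event is the investigator's judgement, extra tests are left to discretion, and nothing shown fixes a retest or its interval.

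A second reply is that a two-week criterion in a four-week study has little room to act. That is correct. A reader might infer that the schedule denies a child first elevated at Visit 4 a stop that retesting would have delivered under this criterion. The dates do not support it: that child cannot reach the threshold before about Day 29. The case for a retest there rests on detecting progression.

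Third, the documents give no sign that such values are common. None of the six dose decreases listed in Section 1.5, nor the seven early terminations in Section 1.3, names transaminases. The documents state no frequency, so no expected count among the 30 patients can be given. Entry to the long-term study falls under a separate protocol (INS011-17-113), and this point does not extend to it.

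**Conclusion.** The point holds as a minor safety gap. Scheduled chemistry cannot show the two-week criterion before End of Study, and the repeat assessment in Section 3.5 starts too late to supply the missing value. For a first elevation at Visit 3, mainly in Cohort 2, a retest could establish the criterion from about Day 16 instead of Day 25 to 31. For a first elevation at Visit 4, its value is earlier sight of progression during about 14 further days of dosing.

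The conclusion assumes that persistence is shown by two draws more than 14 days apart, and that end of Week 2 means Day 14 or Day 15; it is the same for both. It also assumes that the Data Monitoring Charter does not already set a retest interval. It does not mean that the rule can never be met, since Visit 6 or an unscheduled sample can show it, or that the hepatic monitoring as a whole fails, since the three single-draw criteria still act at each scheduled draw.

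**What to change.** In Section 3.5, apply the repeat assessment already written there (ALT, AST, bilirubin, ALP; local laboratory allowed) to any first ALT or AST > 5 × ULN, whether or not a stopping criterion is met. Repeat it at a stated interval, for example within 72 hours and then weekly, until the value resolves or a stopping criterion is met. Add a matching footnote to Table 1. Adding INR to this repeat panel is reasonable, because the fourth criterion uses it. If the Data Monitoring Charter already sets an interval, citing it in Section 3.5 would be enough.

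The cost is a few lines of text and an occasional extra venipuncture in a child with a first value > 5 × ULN.
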